#### **9.3.2 Secondary Outcomes**

Secondary outcome measures will include changes in MRI derived functional connectivity of the subcallosal cingulate to the DLPFC and within the default mode network. Secondary outcome measures will be assessed as the change between baseline and 1-month post-treatment assessment. Exploratory endpoints include biometrics related to sympathetic nervous system activity - Heart Rate, Sweat Chloride, Body Temperature, and Actigraphy.

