## 1. STUDY OBJECTIVES

### 1.1 Primary Objective

To examine the use of accelerated iTBS to treat symptoms of treatment resistant depression in bipolar I disorder and assess changes in neuroimaging biomarkers that may predict treatment response:

Primary Outcome Measure: Change in Montgomery-Asberg Depression Rating Scale (MADRS) score.

Secondary Outcome Measure: Changes in MRI derived functional connectivity of the subcallosal cingulate to the DLPFC and within the default mode network.

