### **3. STUDY DESIGN**

In order to establish feasibility of study design and approach, we will conduct an open label pilot trial of treatment using accelerated iTBS over the left dorsolateral prefrontal cortex (LDLPC) (up to five days, up to 10x/day) using the MagVenture MagPro X100 rTMS System. Participants will have individualized treatment targets that will be produced from structural and functional MRI scans using the software services of Magnus Medical. We will enroll a total of 10 outpatient participants at two participating NNDC centers, the Johns Hopkins University and University of Texas at Austin. The participants will be diagnosed with bipolar I disorder, currently depressed, as determined by a SCID-5 assessment at screening [Day -5/-14]. Participants will be asked to remain on their psychotropic medications for stabilization throughout the screening, baseline, active study and follow-up phases of the study. During active study, changes in medication dosages may be made based on clinical judgment as outlined below. Participants will be required to have an established psychiatrist in order to facilitate ongoing care after the trial.

The expected overall study duration is one year. Each patient will have up to 9 total visits over the course of one month. One visit for consent and screening. One visit for baseline clinical and self-report assessments, MRI scan, and neurocognitive tests. Five consecutive day visits (or less per symptom remission as outlined above via MADRS </=10) of 10 hours each for treatment. Two visits for follow-up. One immediately (up to 5 days) after last day of treatment for clinical and self-report assessments, MRI scan, and neurocognitive tests. And another visit 1-month post-treatment visit for clinical and self-report assessments. All costs for the clinical assessments, MRI scans and TMS treatment related to the conduct of the study will be covered by the study at no expense to the patient. Participants will receive \$500 compensation upon completion of last follow up appointment. This study will offer participants a choice to receive payment/reimbursement through the JHU Greenphire ClinCard Program. The standard Greenphire information sheet will be used to explain the use of Greenphire to participants.

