### **Neuroimaging Biomarkers:**

We will perform structural and resting state functional connectivity MRI with a 3T system prior to active study phase and immediately after active study phase (up to 5 days following final iTBS stimulation). The MRI scans will require about 1 hour in the MRI scanner. During the scan, participants will lie on the table in the magnet while the images are acquired. Instructions may be given through an auditory system. Subjects will wear earplugs and may be fitted for a bite bar to help them to keep their head still during the scans; for studies that enroll older adults, a bite bar will not be used so as to accommodate participants with dentures. These procedures have been used previously in younger and older adults alike, and do not cause undue distress in subjects.

At Baseline and 1 week, our MRI scans will include:

- Anatomical (T1) - 5min
- Resting state fMRI - 24 min
- Resting state ASL - 7 min

-Diffusion-weighted imaging (DWI) - DWI acquisition will take approximately 4 min along 90 non-collinear directions with a b-value=2400s/mm^2.

TOTAL scan time: ~40min

Biomarker measures: We will use a canonical hemodynamic response function (HRF) convolved event-related model with temporal and dispersion derivatives to model the blood oxygen level dependent (BOLD) in the context of a generalized linear model. Separate regressors (convolved with the HRF) will be created for stimulus events in each paradigm. Temporal and dispersion derivatives will be treated as regressors of no interest. A region of interest (ROI) analysis will be performed using our established methods, to identify BOLD-dependent signal change in the dorsolateral prefrontal cortex, subgenual cingulate, and default mode network nodes (right, left). Beta values for each ROI will be extracted for each subject for regression analyses.

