## 6. STUDY PROCEDURES

### 6.1 Schedule of Evaluations

Assessment	Screening (Day -50 to Day -5)	Baseline (Day 0)	Active Study (Day 1)	Active Study (Day 2)	Active Study (Day 3)	Active Study (Day 4)	Active Study (Day 5)	Follow up: Immediate (Day 8 to Day 10)	Follow up: 1-month (Day 30 to Day 40)
Informed Consent	X								
Medical History/Records	X								
MRI Safety Form	X								
Structured Clinical Interview	X								
Clinician Administered Scales	X	X	X	X	X	X	X	X	X
Self-Rated Scales	X	X	X	X	X	X	X	X	X
Biometric Data		X	X	X	X	X	X	X	X
MRI		X						X	
Neurocognitive Measures		X						X	
Study Treatment			X	X	X	X	X		
Continue Medications	X	X	X	X	X	X	X	X	X
Monitor for Adverse Events			X	X	X	X	X		

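### Section 9.3.2 times the MRI connectivity outcome at 1 month, but no MRI is scheduled at the 1-month visit

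*Combined protocol and SAP*

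**What the plan says.** Section 1.1 gives a single secondary outcome and no time point: "Secondary Outcome Measure: Changes in MRI derived functional connectivity of the subcallosal cingulate to the DLPFC and within the default mode network". Section 9.3.2 repeats that outcome and dates it: "Secondary outcome measures will be assessed as the change between baseline and 1-month post-treatment assessment".

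Three sections say when scans are taken:

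- **Section 3** lists an MRI at baseline and then describes two follow-up visits. The first is "One immediately (up to 5 days) after last day of treatment for clinical and self-report assessments, MRI scan, and neurocognitive tests". The second is "And another visit 1-month post-treatment visit for clinical and self-report assessments", with no scan listed.
- **Section 5.1, Neuroimaging Biomarkers,** places the scans "prior to active study phase and immediately after active study phase (up to 5 days following final iTBS stimulation"). The scan list further down in the same section calls the second occasion 1 week.
- **Section 6.1** marks the MRI row under Baseline (Day 0) and under "Follow up: Immediate (Day 8 to Day 10"). The MRI cell under "Follow up: 1-month (Day 30 to Day 40") is empty.

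Section 9.4 analyses connectivity by repeated measures ANOVA with two levels, before and after iTBS. It does not say which visit supplies the second level.

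**The concern.** An outcome definition has to point to data that the schedule will produce. Here the definition points to a visit with no scan. Two things can follow. Read literally, the only named secondary outcome has no data at its stated time. Alternatively, the scan that is taken gets reported under the section 9.3.2 definition, and a change measured within days of stimulation is labelled a 1-month change. That label would suggest a durability nobody measured.

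The imaging outcome is not incidental: section 1.1 makes biomarker change part of the primary objective, and the abstract says the pilot should inform a larger study of factors associated with response. The trial is also open label, so settling the time point before the imaging data are examined avoids an outcome redefined afterwards.

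**Working it through.** The plan gives no power or sample-size figure for this outcome, so there is none to reproduce. The check is a count of scans and a comparison of visit windows.

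**Inputs**

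- Participants: 10, 5 at each of 2 sites (Study Synopsis).
- MRI marks in section 6.1: 2 of 9 visit columns, Baseline and Immediate.
- Section 6.1 windows: Immediate, Day 8 to 10; 1-month, Day 30 to 40.
- Section 6.2 windows for participants who finish treatment early, counted from their last treatment day: immediate, 0 to 5 days; 1-month, 25 to 35 days.
- Time in the scanner: "The MRI scans will require about 1 hour in the MRI scanner" (section 5.1). The same section totals the sequences at about 40 minutes.

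**Scans available**

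| Visit | MRI per participant | Planned scans |
|---|---|---|
| Baseline | 1 | 10 × 1 = 10 |
| Immediate | 1 | 10 × 1 = 10 |
| 1-month | 0 | 10 × 0 = 0 |
| Total | 2 | 20 |

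A change score needs a scan at both ends. Baseline to 1 month: 0 of 10 participants. Baseline to immediate: up to 10 of 10.

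**Could the immediate scan count as the 1-month scan?** The gap between the two windows is:

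- Section 6.1: shortest 30 − 10 = 20 days, longest 40 − 8 = 32 days.
- Section 6.2, early finishers only: shortest 25 − 5 = 20 days, longest 35 − 0 = 35 days.

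The windows never overlap, so it could not.

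**Does section 6.2 add a scan at 1 month?** It repeats the baseline clinical and neurocognitive assessments at both follow-ups and does not mention MRI. Section 3 lists MRI as an item separate from both of those. Section 6.2 also allows follow-up assessments by audio/video link, which could not include a scan.

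**Cost of the alternative, a 1-month MRI:** 10 × 1 = 10 extra scans, and 10/20 = 50% more than planned. At about 1 hour each this is about 10 scanner hours; counting sequence time alone, 10 × 40 min = 400 min, or about 6.7 hours.

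**The case against.** The strongest reply is that this is a drafting slip with little consequence. Sections 3, 5.1 and 6.1 agree on one post-treatment scan shortly after treatment, the two-level contrast in section 9.4 fits two scans, and one sentence in section 9.3.2 is out of line. The data collected would be the same either way, and the mislabelling happens only if someone reports the early scan under the 1-month wording. Much of this stands. A slip is the most economical reading, and it limits the seriousness of the point. But no sentence states the intended time point, and section 9.3.2 is the only place that dates the imaging outcome. Section 9.4 does not correct it.

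A second reply is that section 9.3.2 introduces its list as inclusive, so the 1-month sentence may have been meant for clinical scales repeated at that visit. That is possible, but no such secondary outcome is named in section 1.1 or 9.3.2, and the sentence still governs the one that is. Replacing it would leave nothing in section 9.3 tied to the 1-month visit, which the authors should notice; no named outcome loses its time point.

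A third reply is that the immediate visit is itself described inconsistently: within 5 days of treatment in sections 3, 5.1 and 9.3.1, 1 week in the section 5.1 scan list, and Day 8 to 10 in section 6.1. After treatment ending on Day 5, the 5-day wording admits Days 6 and 7, which section 6.1 does not. This is a fair observation and needs reconciling, but none of these versions is 1 month.

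A broken table does not explain the conflict, because the prose of sections 3 and 5.1 gives the same two-scan schedule. Nor does superseded text: every statement used here is in the current sections.

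**Conclusion.** The concern holds, with high confidence. As section 9.3.2 is written, 0 of 10 participants can contribute the secondary outcome, and this covers both connectivity measures within it (subcallosal cingulate to DLPFC, and within the default mode network). These are counts from the schedule, not an estimated bias, and they assume that all 10 participants enrol and that scans are taken only where sections 3, 5.1 and 6.1 place them.

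The reach is limited. Section 9.3.1 times both primary outcomes, MADRS and YMRS change, at the immediate visit, so they are untouched, and the section 9.4 comparison can run on the scans already scheduled. This should be corrected before the imaging data are analysed; it does not threaten the trial's main result.

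**What to change.** Replace the timing sentence in section 9.3.2 with, for example: *The imaging outcome is the change in functional connectivity from the baseline MRI to the immediate post-treatment MRI, acquired no more than 5 days after the final treatment day.* This is the time point that section 9.3.1 already uses for the primary outcomes. A few words in section 9.4 naming that scan as the post-iTBS level would complete the repair.

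The cost is a text edit, with no added scan or visit. What is given up is any claim about connectivity at 1 month, which the present schedule cannot support anyway.

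If 1-month connectivity is what the investigators want, a 1-month MRI has to be written into sections 3, 5.1 and 6.1. That is a design change costing up to 10 further scans.

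Two lesser matters lie outside this fix. The labels for the immediate visit (up to 5 days, 1 week, Day 8 to 10) should be brought into line, since the primary outcomes are measured at the same visit. The event-related BOLD model in section 5.1 should be reconciled with the resting-state method in section 9.4, keeping the regression on each participant's region-of-interest values.

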## 9.4 Data Analyses

The primary outcome measures will be analyzed using generalized linear mixed models to test if there are significant changes in scores over follow-up. Based on previous work, we will use a compound symmetry or autoregressive covariance structure (based on distribution of residuals) and robust estimation of coefficients to handle violations of model assumptions. Random effects will be included to account for repeated measures on the same participants, and fixed effects of time will be evaluated controlling for fixed effects of age, sex and number of days to reach treatment remission. All post hoc pairwise comparisons will be Bonferroni corrected. Exploratory endpoints related to biometrics will be analyzed in similar fashion.

For assessment of the secondary outcome measures of change in functional connectivity, we will employ a resting-state seed-based functional connectivity approach to assess connectivity between the subcallosal cingulate connectivity to the DLPFC and within the default mode network. For each participant, the correlation coefficients between average blood oxygen level-dependent (BOLD) time series of the seed-region and the BOLD time series of each grey matter voxel within the DLPFC or default mode network will be calculated. The correlation coefficient will be converted to normally distributed z scores by the application of Fisher's r to z transformation. The resulting connectivity maps will be analyzed with repeated measures ANOVA to compare pre-iTBS vs post-iTBS connectivity measures as a within-subject variable, and sex and site as a between-subject covariate.

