propensity of antidepressant response to iTBS by modifying parameters in pulse spacing, dosage and treatment target location (Cazzoli et al., 2009, 2012; Fox et al., 2012; Gamboa et al., 2010; Noh et al., 2012). Applied in a sample of individuals with unipolar (n=20) and bipolar (n=5) treatment resistant depression (TRD), the use of an accelerated iTBS paradigm yielded approximately 90% response and remission rates in depressive symptoms, in both unipolar and bipolar TRD participants (Cole et al., 2020). Of the 5 bipolar TRD participants, all met depression remission criteria within 5 days of treatment, with no hypomania/mania conversion observed during treatment or at follow-up. More recently, SAINT demonstrated evidence of efficacy over sham stimulation in RCT for treatment-resistance depression (Cole et al., 2022). The current study aims to further evaluate the use of an adapted accelerated iTBS protocol for bipolar TRD and neuroimaging biomarkers of treatment response. It will leverage the resources of the National Network of Depression Centers (NNDC), a consortium of academic centers of excellence caring for participants with depression and bipolar disorder, to conduct the pilot study.

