### **Active Study [Day 1-5]:**

TMS sessions will be scheduled in a 5-day sequence, resulting in a total of up to 50 sessions. Prior to each daily treatment series, participants will be asked a short series of

questions assessing medication compliance and substance use, amount and quality of sleep, and any other changes in mood since their last treatment session. We will monitor any medication changes throughout the course of the entire study. Participants will receive up to 10 daily stimulations with active iTBS over the left dorsolateral prefrontal cortex (LDLPFC) (1800 pulses). In the event of depression treatment remission (i.e. MADRS  $\leq 10$ ), treatment emergent mania occurring (defined as an increase of 2 or more points in at least 2 YMRS items), or clinician judgment, LDLPFC treatment will be discontinued and emergent symptoms will be treated by increasing the dose of the participant's anti-manic agent and other pharmacologic measures if necessary as assessed by the onsite clinician.

If participants do not experience a significant increase in manic/hypomanic symptoms ( $\geq 2$  item increase of 2 or more points on the YMRS scale), LDLPFC treatment will continue until MADRS  $\leq 10$  or the end of the 5-day treatment series is reached.

Each session will be separated by a 50-minute break. This separation between stimulation sessions decreases the risk of associated TMS side effects (e.g. irritation from the device, headache). The modified PANAS (items 3, 9, 11, 17, 18, 19) will be administered between every stimulation session to assess for any potential shift towards (hypo)mania. If a significant increase ( $\geq 2$  item increase of 2 or more points) is observed, the YMRS will be administered.

Active study clinical measures collected at beginning and end of each treatment day (unless where noted) will include:

1. YMRS (AM and PM)
2. MADRS (AM, PM, and as clinically indicated)
3. Daily Check-In Form (AM only)

Active study self-report measures collected at end of each treatment day will include:

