4. MADRS-S
5. C-SSRS

If participants do not remit but respond (>/=50% decrease on the MADRS from baseline) to treatment by the end of the acute, 5-day treatment series, they may be referred to a TMS clinic or further treatment per their outpatient psychiatrist.

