## **7.2 Management of Adverse Events**

**Seizure:** In the unlikely occurrence of a suspected seizure, participation will be discontinued and the participants will be provided with a referral to outpatient care. Any seizure that theoretically could occur would likely be self-limited and lead to no residual neurological impairment. Seizures induced by rTMS are rare, brief and don't result in sequelae, with no events of status epilepticus ever being reported (Rossi et al., 2009).

**Mania:** In the event of emergent mania symptoms (defined as an increase of 2 or more points in at least 2 YMRS items), or clinician judgment, treatment will be discontinued and emergent symptoms will be treated by increasing the dose of the participant's anti-manic agent and other pharmacologic measures if necessary as assessed by the onsite clinician.

**Suicide:** If any study personnel believe a participant is at suicide risk, the site PI will be notified immediately and an emergency consultation between them, clinical staff, and the participant will be had. If the study team considers it necessary, the patient will be referred for emergency psychiatric treatment.

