### **9.3 Outcomes**

#### **9.3.1 Primary Outcome**

The primary outcome measures for this study will be change in MADRS scores. The MADRS is a clinical assessment tool used to rate a patient's level of depression and is the standard scale used for depression research studies. The YMRS will be used as a second primary outcome measure to assess any changes in symptoms of mania over the course of treatment. The YMRS is a clinical assessment tool used to assess the presence and severity of manic symptoms. The primary outcome measures will be assessed as the change between baseline and immediate (up to 5 days after last day of treatment) post-treatment assessment.

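### The primary MADRS and YMRS models adjust for days to remission, a post-baseline quantity taken from the MADRS itself that non-remitters do not have

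*Combined protocol and SAP*

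**What the plan says.** Section 9.4 fits generalized linear mixed models to the primary outcomes, and "fixed effects of time will be evaluated controlling for fixed effects of age, sex and number of days to reach treatment remission". Section 9.3.1 makes change in MADRS primary and adds: "The YMRS will be used as a second primary outcome measure to assess any changes in symptoms of mania over the course of treatment". Both are assessed from baseline to the immediate post-treatment visit.

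Remission is defined by the MADRS. Section 3 plans five treatment days, "or less per symptom remission as outlined above via MADRS </=10", and section 6.2 has the scale rated morning and evening on each treatment day.

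The protocol expects that some participants will not remit:

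- Section 6.2 (Active Study) continues treatment until the MADRS threshold is met "or the end of the 5-day treatment series is reached".
- Section 6.2 (Follow-up), repeated in section 8, provides for a group without remission: "If participants do not remit but respond (>/=50% decrease on the MADRS from baseline".
- Section 7.2 ends stimulation early for another reason: "In the event of emergent mania symptoms (defined as an increase of 2 or more points in at least 2 YMRS items".
- Section 8 allows withdrawal at any time.

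No section assigns these participants a days-to-remission value, defines an analysis set or gives a missing-data rule.

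**The concern.** A covariate in a model of change should be known at baseline or at least exist for everyone analysed. This one is neither. It is measured after treatment begins, it is a function of the primary outcome, and it is undefined for the participants who do worst on that outcome.

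The usual software default is to drop records with a missing covariate. Both primary models would then be restricted to people selected for having reached a MADRS of 10 or less, and the estimated MADRS change would be biased toward benefit. The YMRS model would lose anyone stopped for emergent mania before remitting, who are the participants that outcome is meant to reveal. Sections 9.1 and the abstract say the results are to motivate a larger, adequately powered study, so a remitters-only estimate would carry forward into its planning.

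**Working it through.** The plan gives no power, standard deviation or effect size, so there is no figure of its own to reproduce. The check has four steps.

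**1. How likely is at least one non-remitter?** Inputs: n = 10 (synopsis). Section 2.2 reports that the earlier study "yielded approximately 90% response and remission rates in depressive symptoms, in both unipolar and bipolar TRD participants" and "Of the 5 bipolar TRD participants, all met depression remission criteria within 5 days of treatment". With remission probability p, the chance of at least one non-remitter is 1 − p^10.

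- p = 0.90: 1 − 0.90^10 = 65%.
- p = 0.70: 1 − 0.70^10 = 97%.
- The exact two-sided 95% lower limit for 5 of 5 is 0.025^(1/5) = 0.478. At p = 0.478: 1 − 0.478^10 = 99.9%.

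**2. MADRS, if non-remitters are dropped.** The inputs below are assumptions, not plan figures: baseline N(29, 5) truncated at 20 or more (the entry threshold), SD of change 8, measurement SD 3, ten morning and evening looks, treatment stopped at the first score of 10 or less, true mean change varied from −10 to −30. There were 400,000 simulated participants per setting.

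| Remission | Mean change, all | Mean change, remitters only | Overstatement |
|---|---|---|---|
| 89% | −19.5 | −19.6 | 0.1 |
| 76% | −18.2 | −18.7 | 0.5 |
| 58% | −16.1 | −17.6 | 1.5 |
| 48% | −14.7 | −17.0 | 2.3 |
| 37% | −13.0 | −16.4 | 3.4 |
| 20% | −9.2 | −15.2 | 6.0 |

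A second simulation used different assumptions: baseline about N(30, 5) floored at 20, mean fall 10 to 28 with SD 7 to 8, rating error SD 2.5, and 4,000 trials of 10 per setting. It shows the same pattern.

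| Average non-remitters of 10 | All | Remitters only | Overstatement |
|---|---|---|---|
| 1.6 | −21.2 | −21.5 | 0.3 |
| 3.1 | −19.4 | −20.6 | 1.2 |
| 4.6 | −17.1 | −19.5 | 2.4 |
| 6.6 | −13.6 | −18.0 | 4.4 |
| 8.2 | −9.5 | −16.6 | 7.1 |

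These are averages, and a single trial can differ. In one simulated trial with 3 non-remitters, the time effect was −21.85 (robust SE 1.54) with all 10 participants and −21.77 (SE 2.20) with the 7 remitters. There the visible cost was precision, not bias.

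**3. YMRS, if non-remitters are dropped.** The mania trigger is at least 2 items each up by at least 2 points, so at least 2 × 2 = 4 points. Suppose that rise persists to the immediate visit and everyone else is unchanged. One such non-remitter gives a mean change of 4/10 = +0.4 if kept and 0.0 if dropped. Two give 8/10 = +0.8 against 0.0.

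**4. If non-remitters are given a value instead.** Write each score as intercept + time effect + γ·d + participant effect + error, where d is days to remission. Within a participant, γ·d is the same at baseline and at the immediate visit, so it cancels from the difference. The coding therefore cannot affect the time contrast when both scores are present. The simulations agree:

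- In complete data, coding non-remitters 5, 6 or 10 moved the contrast by 0.00 (150 simulated trials of 10 per setting).
- With unbalanced daily scores added, under compound symmetry or an autoregressive structure, the contrast was unchanged to rounding error.
- With one of 10 follow-up scores missing, it moved by a median of 0.1 to 0.2 points, with the mean essentially unchanged.

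The term is therefore inert for the primary contrast in complete data if values are filled in, and harmful if they are not.

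**The case against.** The case on the other side has six parts.

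- **The bias needs listwise deletion, which the plan does not state.** This stands as a limit. With only 10 participants an analyst would probably notice the loss, and could supply a code. But that code would be chosen after seeing the data, and step 4 shows it would do nothing for the complete-data contrast.
- **Near the documented remission rate the bias is negligible.** This stands. The 37% and 20% rows lie below even the 48% lower limit and are hypothetical. At 48% the 2.3-point bias is slightly below the standard error of a mean of 10 on the assumed SD (8/√10 = 2.5). However, the bias acts in one direction, and the 48% limit rests on only five bipolar participants.
- **The MADRS figures depend on assumed inputs**, including the shape of the fall over the week. This also stands. Direction and pattern agree across two sets of assumptions, but the decimals are illustrative.
- **Mania would not vanish from the record.** Adverse events are reported (section 7.3), reasons for discontinuation are recorded (section 8), and unresolved hypomania feeds the stopping rule (section 9.2). Emergent symptoms are also to be treated, so the 4-point rise may not persist, and a withdrawn participant may lack the follow-up score anyway. All true, but none of it restores the participant to the primary YMRS model.
- **The term may be meant to adjust for treatment exposure**, because treatment stops at remission. The plan does not say so. Using days treated would give a participant stopped for mania on day 2 the same value as one who remitted on day 2.
- **This is a small open-label feasibility pilot with no power claim.** That limits the severity. It does not justify an undefined covariate in the primary model.

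**Conclusion.** The concern holds. The primary model in section 9.4 contains a post-baseline covariate derived from the MADRS that is undefined for participants the protocol itself foresees, with no rule for handling them. The chance that the problem arises is 65% at 90% remission and higher at lower rates.

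Its effect on the estimate depends on two things: whether non-remitters are dropped (assumed, not stated) and how many there are. If they are dropped, improvement on the MADRS is overstated by roughly 0.1 points at 89% remission and 2.3 points at 48% under the stated assumptions. The loss from the YMRS model does not need a low remission rate; it needs only one participant stopped for mania before remitting. There is no claim that standard errors are too small. This should be fixed before analysis, but it does not invalidate the trial.

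**What to change.** In section 9.4:

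1. Delete the days-to-remission term from the primary model, keeping age and sex.
2. State that all treated participants are analysed for both primary outcomes whatever their remission status.
3. Report time to remission separately and descriptively, with non-remitters censored at their last on-treatment MADRS assessment: the end of the 5-day series, or earlier if treatment stopped earlier. List stops for emergent mania separately in that report, since they are not the same as reaching day 5 without remission.

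The cost is one or two sentences in section 9.4, with no new data and no more participants. In complete data, removing the term leaves the baseline-to-immediate contrast identical to a fit on all participants with any coding, so nothing is lost.
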